#### **14.1.5 Interim Analysis**

##### **14.1.5.1 Monitoring of Efficacy**

One interim analysis will be conducted on each cohort. Each Interim Analysis will occur once 10 patients have been followed for at least six months on that cohort. Accrual will not stop for this interim analysis. If at least 3 out of the first 10 evaluable patients are alive and progression free at 6 months, that cohort will proceed to full accrual. If 2 or fewer of the

CONFIDENTIAL

This document is confidential. Do not disclose or use except as authorized.

first 10 evaluable patients have remained progression free at six months, further accrual will be stopped to that cohort and that cohort will be discontinued. Under this stopping criterion, the chances of stopping a cohort early is 0.5 and 0.048 under the null and alternative respectively. The stopping rule for the interim analysis was designed to optimize for a low type II error.

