#### **5.5 Total Study Duration**

Cohort 1: It is projected that accrual to this cohort will be completed within 24 months after the first participant is enrolled.

Cohort 2: It is projected that accrual to this cohort will be completed within 24 months after the first participant is enrolled.

The final analysis for the primary objective is expected 12 months after the last participant has initiated study therapy. Additional survival follow-up may continue after the primary analysis of survival.

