#### **14.1.4 Power and Sample Size**

This study will determine whether nivolumab monotherapy and/or nivolumab plus ipilimumab significantly delays progression among patients with recurrent meningioma based on a primary endpoint of PFS-6 with a planned sample size of 25 patients per cohort. Effective therapy for patients with atypical or anaplastic meningioma who progress after surgery and radiotherapy does not exist. A recent meta-analysis of salvage medical therapies for recurrent WHO grade II/III meningiomas refractory to surgery or radiation therapy revealed a weighted PFS-6 of 26% (95% CI: 19.3-32.7%) and 29% (95% CI: 20.3%, 37.7%) among those with grade I meningiomas that progressed after prior radiation therapy.(20) With a sample size of 25 patients per cohort, our study will have 90% power to detect a PFS-6 increase of 25% (26% vs. 51%) using a one-sided significance level of 0.10 (exact alpha=0.089). At the final stage of analysis, the null hypothesis will be rejected and nivolumab monotherapy or nivolumab plus ipilimumab therapy will be considered worthy of further investigation for patients with atypical/anaplastic meningioma if at least 10 patients are progression-free at the six months timepoint.

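### The futility look waits for six months on 10 patients with accrual open, although a stop is certain at the eighth established failure; closing then is a cheap but modest improvement

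*Combined protocol and SAP*

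**What the plan says.** Section 14.1.5.1 plans one efficacy look per cohort: "Each Interim Analysis will occur once 10 patients have been followed for at least six months on that cohort". It adds: "Accrual will not stop for this interim analysis". A cohort continues if at least 3 of its first 10 evaluable patients are alive and progression-free at six months. It closes if 2 or fewer of the "first 10 evaluable patients have remained progression free at six months, further accrual will be stopped to that cohort". The stated chances of stopping are 0.5 under the null and 0.048 under the alternative, and the section says that the rule was built for a low type II error.

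Section 14.1.4 sets 25 patients per cohort, PFS-6 of 26% against 51%, and success at 10 or more progression-free. Section 5.5 gives the pace: "Cohort 2: It is projected that accrual to this cohort will be completed within 24 months after the first participant is enrolled".

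Two further sections decide when a failure is known. Section 14.1.6.1 requires confirmation of progression for the primary endpoint. Section 11.4 places the confirming MRI 12 weeks after a first radiologic progression within six months, for patients who appear to benefit, tolerate therapy and have no tumor-related neurologic decline. Confirmed progression is dated back to the first scan.

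No section provides for closing earlier. The safety committee text in Section 12.2 covers toxicity and accrual and sets no efficacy trigger.

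**The concern.** Having 2 or fewer of 10 patients progression-free is the same event as having 8 or more of 10 fail. Once eight failures are established, nothing that happens to the other two can rescue the cohort, even if they have not yet enrolled. As written, accrual nevertheless runs on until the tenth patient reaches six months. Patients who enter in between join a cohort whose closure is already settled. For cohort 2, Section 2.5 says that the overall safety of the combination in this setting is not known. That makes avoidable entries worth preventing if it can be done without statistical cost.

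**Working it through.** **1. The plan's own figures.** With X binomial (n = 10), P(stop) = P(X ≤ 2):

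- p = 0.26: 0.74^10 + 10(0.26)(0.74^9) + 45(0.26²)(0.74^8) = 0.0492 + 0.1730 + 0.2735 = 0.496 (stated 0.5).
- p = 0.51: 0.0008 + 0.0083 + 0.0389 = 0.048 (stated 0.048).

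The final rule of at least 10 of 25, taken alone, gives alpha 0.0893 and power 0.9036, which matches Section 14.1.4. With the interim stop included these are 0.0823 and 0.8800.

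**2. Effect of closing at the eighth established failure.** Closure then happens exactly when X ≤ 2, as before. The two stopping probabilities, alpha and power are therefore identical with and without it. This needs failures that cannot later be reversed.

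**3. How many patients enter while waiting.** The accrual rate is 25/24 = 1.04 per month. With regular entry the tenth patient enters at 9/1.04 = 8.64 months and the look falls at 14.64 months, when 16 are enrolled. So about 6 enter after the tenth.

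**4. How many of those are avoidable.** This was simulated for cohorts that stop under the 26% null. Assumptions: random (Poisson) entry at the rate above, exponential PFS with 26% at six months, and detection at the next 8-weekly scan. A failure is a true progression before six months. The documents do not say what share of progressions awaits the 12-week MRI, so the range is shown.

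| Share awaiting confirmation | Eighth failure known before the look | Mean patients spared per stopped cohort |
|---|---|---|
| None | 96% | about 3 (2.9 to 3.1 across runs) |
| Half | not tabulated | about 1.5 (1.5 to 1.6) |
| All | 49% | 0.7 to 0.8 |

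If all wait, about two thirds of stopped cohorts (66%) spare nobody.

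Sensitivity:
- Regular entry gives 3.6 (none) and 1.1 (all).
- Accrual of 25 in 12 months, an assumption, gives 4.0 to 4.6 (none) and 0.5 (all).
- If the written look would itself wait for pending confirmations, on which the plan is silent, the saving rises to 1.8 (half) and 1.2 (all).

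**5. Per cohort started.** Multiply by the chance of stopping.

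- Null: 0.496 × 0.77 = 0.4 (all wait) to 0.496 × 3 = 1.5 (none wait).
- Alternative, where the simulated savings per stopped cohort are 0.37 and 2.09: 0.048 × 0.37 = 0.02 to 0.048 × 2.09 = 0.10.

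**6. What if unconfirmed progression were counted?** Suppose a fraction m of truly progression-free patients first read as progressed. The success rate that is tallied becomes p(1 − m). With m = 10%:

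- Null: 0.26 × 0.9 = 0.234, and P(stop) rises from 0.496 to 0.574.
- Alternative: 0.51 × 0.9 = 0.459, and P(stop) rises from 0.048 to 0.090. It is 0.066 at m = 5% and 0.155 at m = 20%.

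The value of m is an assumption. Section 5.6 reports apparent progression before benefit in about 10% of subjects in a Phase 1 nivolumab study, which is the only guide.

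**The case against.** The strongest reply is that a single fixed look with accrual open is a deliberate choice. Its stopping probabilities reproduce, nothing in the plan contradicts it, and the gain is small under the plan's own endpoint. The committee may also see response information up to four times a year, and the sponsor may terminate the study.

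Much of this stands. No figure is wrong, and with full confirmation the mean saving is below one patient. But committee review and sponsor discretion are not triggers. Nor is the all-confirmed case the likely one. Under Section 11.4 a patient with significant tumor-related neurologic decline is a treatment failure without waiting, and Section 14.1.2.2 counts death as an event.

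A reader might infer that about three patients are spared per cohort at no inferential cost. The documents do not support that pairing. Three patients requires progression to count at the first scan, whereas Section 14.1.6.1 requires confirmation and Section 11.4 allows a first progression to revert to stable disease or response. Counting unconfirmed progression would raise the chance of wrongly stopping an active regimen (step 6), against the stated aim of a low type II error. The no-cost claim holds only for confirmed or non-radiologic failures, and the saving is then smaller.

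**Conclusion.** The point holds as a cheap improvement, not as an error. The look is later than the decision requires, and closing at the eighth established failure leaves every operating characteristic unchanged. The mean benefit per stopped cohort under the null lies between about 0.7 and 3 patients, depending on how many progressions wait for confirmation. It arises only in cohorts that stop.

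The size rests on assumed exponential PFS, the projected accrual rate and random entry. The pauses of the cohort 2 safety lead-in are not in these figures; a simple version with two 42-day pauses barely changed them. The logic of step 2 rests on none of these.

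A reader might also take the point to apply to both cohorts. Section 1 opens cohort 2 only after cohort 1 has finished enrolling, so in practice it concerns cohort 2.

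**What to change.** Add to Section 14.1.5.1:

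> If at any time 8 of the first 10 evaluable patients in a cohort (the same 10 used for the interim look) have died within six months of starting study therapy, or have progression dated within that period that is established for the primary endpoint, accrual to that cohort closes at once. Established means confirmed radiologic progression, or clinical progression that needs no confirmation under Section 11.4. Radiologic progression still awaiting confirmation does not count. The six-month look remains for all other cases.

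Define evaluable for this purpose, since Section 14.1.5.1 does not, and make the 10 patients who trigger the look the same 10 who are counted. Section 14.2 already uses treated participants for efficacy, so the first 10 treated would be a natural choice.

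The cost is this text and a running tally. The study is open-label with investigator-assessed progression, and Section 14.1.5.2 already has a comparable running count for toxicity. The downside is slightly fewer patients for estimation in a cohort that is being discontinued anyway.

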#### 14.1.5.2 Monitoring of Toxicity (Stopping Rule for Unexpected Toxicity)

A futility monitoring boundary of toxicity will be assessed separately for this study. Unacceptable toxicity rates of 20% or less are considered desirable. Patients will be monitored for adverse events and if, at any time during the course of the study, 2 out of the first 10 patients in a cohort - or more than 20% after the first 10 patients in that cohort - experience a grade 4 or higher non-hematologic adverse event considered related to study treatment, accrual for that cohort will be temporarily suspended to allow for full investigation of all adverse events by the study team.

### 14.1.6 Analysis Endpoints

Efficacy and safety endpoints that will be evaluated for within- and/or between-treatment differences are listed below, followed by the descriptions of the derivations of selected endpoints.

#### 14.1.6.1 Efficacy Endpoints

Efficacy endpoints that will be evaluated for are listed below, followed by the descriptions of the derivations of selected endpoints.

The primary efficacy endpoint for this study is PFS-6, defined as the proportion of subjects in the analysis population who remain progression-free for at least six months following initiation of study therapy. Response for the primary analysis will be determined by the investigator assessment, and a confirmation assessment is required per iRANO.

Secondary efficacy endpoints include: (1) ORR defined as the proportion of subjects in the analysis population who have complete response (CR) or partial response (PR) using iRANO criteria as well as duration of response, defined as time from first iRANO response to disease progression in subjects who achieve a PR or better; (2) progression-free survival (PFS), defined as the time from allocation to the first documented disease progression according to iRANO or death due to any cause, whichever occurs first; and (3) overall survival (OS). Secondary endpoints will be assessed using standard descriptive statistics and the Kaplan Meier method to estimate median OS and PFS and rates at times of interest. Duration of response (DOR), defined as the time from first documented disease response to progression or death, whichever comes first.

Additional supportive analyses of best overall response rate, duration of response, and PFS will be conducted using iRANO criteria, in which a confirmation assessment of disease progression must be obtained at least 4 weeks after the initial disease assessment indicating progressive disease.

Nominal p -values may be computed for efficacy analyses as a measure of strength of association between the endpoint and the treatment effect rather than formal tests of hypotheses. Unless otherwise stated, all statistical tests will be conducted at the  $\alpha=0.05$  (2-sided) level.

CONFIDENTIAL

This document is confidential. Do not disclose or use except as authorized.

**14.1.6.2 Safety Endpoints**

The primary safety endpoints are AEs graded using CTCAE (Version 4.0) criteria. Safety will be assessed by quantifying the toxicities and grades experienced by subjects who have received nivolumab, including serious adverse events (SAEs). Other safety endpoints include laboratory safety assessments, KPS status, vital signs and physical examinations.

Adverse experiences (specific terms as well as system organ class terms) and predefined limits of change in laboratory, and vital sign parameters that are not pre-specified as events of interest will be summarized with descriptive statistics (counts, percentage, mean, standard deviation, etc.).

Continuous measures such as changes from baseline in laboratory, and vital signs parameters that are not pre-specified as events of interest will be summarized using descriptive statistics (mean, standard deviation, etc.) for baseline, on-treatment, and change from baseline values.

**14.1.6.3 Summary of Demographic and Baseline Characteristics**

Baseline characteristics will be assessed by the use of tables and/or graphs for this study. No statistical hypothesis tests will be performed on these characteristics. The number and percentage of subjects screened, allocated to treatment, the primary reasons for screening failure, and the primary reason for discontinuation will be displayed. Demographic variables (e.g., age, gender), baseline characteristics, primary and secondary diagnoses, and prior and concomitant therapies will be summarized by treatment either by descriptive statistics or categorical tables.

**14.1.6.4 Analysis of Immunocorrelative Data**

Descriptive statistics (mean, SD, CV% or median [range]) will be performed on correlative immune biomarker data. Specific statistical analyses on these data will depend on the amount and quality of the data obtained as well as the overall success of the treatment. In addition, longitudinal analyses of PBMC immune response kinetics and circulating cytokines to nivolumab therapy will be presented graphically and descriptively at each time point. Changes in the magnitude of the response relative to pre-treatment after nivolumab therapy will be summarized descriptively. Changes in response between pre-treatment and prior to initiation of cycle 5 of nivolumab therapy will be assessed using the Wilcoxon signed-rank test.

**14.1.6.5 Neurologic Assessment in Neuro-Oncology (NANO) Scale**

The evaluation of neurologic function as defined by the NANO scale will be assessed as an exploratory objective in this study and evaluated by assessing mean changes from baseline in the level of function score for each domain.

**14.1.6.6 Compliance (Medication Adherence)**

A day within the study will be considered an On-Therapy day if the subject receives the study medication infusion. The number of Days Should be on Therapy is the total number of days from the first day of study medication to the date of the last dose of study medication. For each subject, percent compliance will then be calculated using the following formula:

Percent Compliance =

CONFIDENTIAL

This document is confidential. Do not disclose or use except as authorized.

(Number of Days Should be on Therapy/Number of Days on Therapy) x 100

Summary statistics will be provided on percent compliance by treatment group for the FAS population.

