## 5. TREATMENT PLAN

### 5.1 Cohort 1: Nivolumab Monotherapy Treatment Regimen

Nivolumab will be administered every 2 weeks\*, with 14 consecutive days defined as a treatment cycle.

Dosing window\*: There is an administration window of -2/+5 days for Nivolumab administrations; however, participants may be dosed no less than 12 days (11 non-dosing days) between doses.

Labs/assessments window: Labs/assessments may be performed up to 3 days prior to Nivolumab doses.

\* NOTE: Participants who have received active study therapy for  $\geq$  6 months will be allowed the option to adjust their Nivolumab dosing schedule from 240 mg once every 2 weeks (-2/+5 days) to 480 mg once every 4 weeks (+/- 1 week).

Counting of days will not be continuous on study. In the event of a treatment delay due to a toxicity, the current cycle will be extended until the criteria to resume treatment are met. The day of treatment restart will be the participant's subsequent cycle's Day 1.

If treatment with study medication is delayed  $>$  6 weeks, the participant must be permanently discontinued from study therapy, except as specified in Section 6.4.

Treatment will be administered on an outpatient basis. Reported adverse events and potential risks are described in Section 7. Appropriate dose modifications are described in Section 6. No investigational or commercial agents or therapies other than those described below may be administered with the intent to treat the participant's malignancy.

For details regarding drug storage, preparation, administration, and use time please refer to Section 8 of the protocol and the current BMS-936558 (nivolumab) Investigator Brochure.

Nivolumab is to be administered as an IV infusion over 30 minutes (window of -10 / + 30 min). At the end of the infusion, flush the line with a sufficient quantity of normal saline.

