### **5.2.3 Nivolumab Therapy**

Nivolumab will initially be administered every 3 weeks at a dose of 3 mg/kg for four doses in combination with ipilimumab, and then will be administered at a flat dose of 480 mg every four weeks until study therapy discontinuation.

Dosing window: There is an administration window of -2/+5 days for Nivolumab administrations.

Labs/assessments window: Labs/assessments may be performed up to 7 days prior to Nivolumab doses.

Counting of days will not be continuous on study. In the event of a treatment delay due to a toxicity, the current cycle will be extended until the criteria to resume treatment are met. The day of treatment restart will be the participant's subsequent cycle's Day 1.

If treatment with study medication is delayed > 12 weeks, the participant must be permanently discontinued from study therapy, except as specified in Section 6.4.

Treatment will be administered on an outpatient basis. Reported adverse events and potential risks are described in Section 7. Appropriate dose modifications are described in Section 6. No investigational or commercial agents or therapies other than those described below may be administered with the intent to treat the participant's malignancy.

For details regarding drug storage, preparation, administration, and use time please refer to Section 8 of the protocol and the current BMS-936558 (nivolumab) Investigator Brochure.

Nivolumab is to be administered as an IV infusion over 30 minutes (window of -10 / + 30 min). At the end of the infusion, flush the line with a sufficient quantity of normal saline. On treatment days when both nivolumab and ipilimumab are administered, nivolumab will be administered first with a 30 minute observation window before starting ipilimumab.

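### The percent-compliance formula in Section 14.1.6.6 is upside down and divides calendar days by infusion days, so the planned descriptive adherence summary cannot be interpreted

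*Combined protocol and SAP*

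**What the plan says.** Section 14.1.6.6 defines two quantities and a ratio. For the first: "A day within the study will be considered an On-Therapy day if the subject receives the study medication infusion". The second, the number of days for which treatment was expected, covers the "total number of days from the first day of study medication to the date of the last dose of study medication". The ratio is "Number of Days Should be on Therapy/Number of Days on Therapy) x 100". It is to be summarised "by treatment group for the FAS population".

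Dosing is intermittent throughout. In Cohort 1 (Section 5.1), "Nivolumab will be administered every 2 weeks", "with 14 consecutive days defined as a treatment cycle", with an option after at least 6 months to move to a 4-weekly schedule. In Cohort 2 (Section 5.2.3), "Nivolumab will initially be administered every 3 weeks at a dose of 3 mg/kg for four doses in combination with ipilimumab"; afterwards it "will be administered at a flat dose of 480 mg every four weeks until study therapy discontinuation".

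Three other places matter. Section 14.1.6.7 defines extent of exposure separately, as the number of cycles with an infusion, on the treated participants. Section 14.2 lists the Enrolled, Treated, Response-Evaluable, Biomarker and NANO populations and no FAS. Section 14 says that no separate SAP will be issued, so this paragraph is the only definition of compliance.

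**The concern.** There are two separate errors. The first is inversion: the expected amount is divided by the actual amount, so giving fewer infusions over the same span makes the figure larger. The second is a mismatch of units. The expected amount is in calendar days and the actual amount is in infusion days. For a once-daily drug the units would agree and only the inversion would remain. For an infusion every 2 to 4 weeks, most days in the span can never be on-therapy days, however well the participant adheres.

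What is at stake is one planned table. An analyst who follows the text must report percentages far above 100, driven mainly by dosing interval and number of doses. An analyst who does not follow it has no stated rule to use instead. The named analysis population also does not exist in the plan.

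**Working it through.** The plan states no compliance value, so there is no figure to reproduce. The check applies the printed definitions to simple dosing histories.

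**Inputs from the documents.** The ratio and its two terms (Section 14.1.6.6); a 14-day interval in Cohort 1 (Section 5.1); in Cohort 2, four doses at 21-day intervals, then 28-day intervals (Section 5.2.3). The denominator is read as the number of On-Therapy days, that is, infusion days.

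**Assumptions.** The number of doses is not in the documents. The main example uses 13 doses on days 1, 15, ..., 169, about six months; a range follows. The span counts both end days.

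**Formula as printed.** Percent = (last dose day − first dose day + 1) / infusions given × 100.

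**Cohort 1, every dose on time.** With n doses the span is 14(n − 1) + 1 days.

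| Doses | Span (days) | Printed compliance |
|---|---|---|
| 1 | 1 | 1/1 = 100% |
| 2 | 15 | 15/2 = 750% |
| 4 | 43 | 43/4 = 1075% |
| 13 | 169 | 169/13 = 1300% |
| 26 | 351 | 351/26 = 1350% |
| 52 | 715 | 715/52 = 1375% |

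The limit is 1400%. Without the extra day in the span, 13 doses give 168/13 = 1292%, so the day-count convention hardly matters.

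**Cohort 2, every dose on time.** Four combination doses on days 1, 22, 43 and 64 give 64/4 = 1600%. Adding four maintenance doses, the first assumed 3 weeks after the last combination dose (days 85, 113, 141, 169), gives 169/8 = 2113%.

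**Permitted Cohort 1 switch, no dose missed.** Thirteen 2-weekly doses to day 169, then seven 4-weekly doses to day 169 + 7 × 28 = 365, give 365/20 = 1825%. Staying on the 2-weekly schedule over the same span gives 27 doses (1 + 26 × 14 = 365) and 365/27 = 1352%. Both participants are fully adherent.

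**Departures from the 13-dose schedule.**

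| History | Printed compliance | Change from 1300% |
|---|---|---|
| One dose missed between first and last | 169/12 = 1408% | up |
| Three doses missed between first and last | 169/10 = 1690% | up |
| All 13 given, one 28-day delay | 197/13 = 1515% | up |
| Final dose missed | 155/12 = 1292% | slightly down |
| Stopped after two doses | 15/2 = 750% | down |
| Stopped after one dose | 1/1 = 100% | down |

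The last three fall because the numerator ends at the last dose actually given, so doses missed at the end drop out of both terms.

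**Swapping the terms is not enough.** 13/169 = 7.7% for perfect adherence. The expected term must also be a count of scheduled infusions.

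**Infusions received over infusions scheduled.** With 13 scheduled: 13/13 = 100%; one missed, wherever it falls, 12/13 = 92.3%; three missed, 10/13 = 76.9%.

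**The case against.** The strongest reply is that this is a visible slip in a minor table. Any value above 100% would be noticed at once. Extent of exposure in Section 14.1.6.7 already gives a sound count of cycles delivered. Infusion start and stop times are documented (Section 10 calendar footnotes), so a correct figure can be computed later. Section 14 also lets changes to non-confirmatory analyses be listed in the study report. All of this stands and is why the point is minor. It does not remove the point: the printed rule gives a wrong result, no other section corrects it, and the exposure count has no expected-dose denominator, so it cannot stand in for compliance.

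Two stronger readings are tempting, and the documents do not support them.

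- A reader might infer that the ordering is simply reversed, so that whoever misses most infusions scores highest. That holds only for doses missed or delayed between first and last dose, at equal span and on one schedule. A participant who stops after two of 13 doses scores 750%, below the 1300% for full adherence.
- A reader might infer that the PFS-6 result, or a comparison of the cohorts, depends on this figure. Compliance is not an objective (Section 1) or an endpoint (Section 14.1.2). It does not enter the decision rule (Section 14.1.4) or the interim rule (Section 14.1.5.1), and it defines no analysis population (Section 14.2). Section 14.1 judges each arm against historical controls, and no section plans a comparison of compliance between cohorts.

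It is also fair to object that a bare received-over-scheduled ratio is ambiguous. Sections 5.1, 5.2.3 and 6.3 move the schedule when treatment is delayed, and Sections 6 and 6.4 allow some Cohort 2 participants to continue on nivolumab alone. The replacement text has to deal with this.

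**Conclusion.** The formula is wrong as written. It is inverted, its two terms are in different units, and it names an undefined population. Perfect adherence reads 1300% in the assumed 13-dose Cohort 1 example, 100% to 1375% over 1 to 52 doses, and 1600% for the four Cohort 2 combination doses. Departures from schedule move the figure in either direction depending on where they fall, and a permitted schedule change moves it with no dose missed. The existence of the error needs no assumption beyond the printed definitions and dosing intervals; only the sizes depend on the assumed dose counts. The damage is confined to the descriptive compliance summary.

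**What to change.** In Section 14.1.6.6, replace the formula and its two day-count definitions with: percent compliance = (infusions received / infusions scheduled between first dose and end of treatment under the participant's protocol schedule) × 100. Report it by agent and by phase (combination, maintenance) in Cohort 2, on the Treated participants of Section 14.2 in place of the FAS. The window should close at end of treatment rather than at the last dose given; otherwise doses missed at the end disappear again.

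The same text should state three counting rules:

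- **Permitted delays.** Say whether scheduled doses follow the extended cycles or the original calendar. With 13 doses and one 28-day delay (days 1 to 197), extended cycles give 13/13 = 100%. The original calendar has 1 + 196/14 = 15 scheduled doses and gives 13/15 = 86.7%. Either can be defended, but they answer different questions.
- **Cohort 1 schedule switch.** Say that the scheduled count uses the interval in force at each point, and from what date.
- **Move to nivolumab monotherapy in Cohort 2.** Say whether ipilimumab doses not given after the move stay in the scheduled count for ipilimumab.

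The cost is a short text change. The infusion records it needs are already collected, and no endpoint, sample size or decision rule changes.
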